### 5.4.2 Stratification

Randomization will be stratified by type of ART (PI/r/c or NRTI/NNRTI-based) and CD4 nadir (> 300 or < 300) at screening. In this way, the distribution of these parameters between the study groups will be balanced.

### 5.4.3 Blinding

A double-blind/masking technique will be used. Reformulated raltegravir and placebo will be packaged identically so that blind/masking is maintained. The subject, the investigator and Sponsor personnel or delegate(s) who are involved in the treatment or clinical evaluation of the subjects are unaware of the group assignments.

The Pharmacy Service will dispense the raltegravir /placebo to the patient.

The study drug (raltegravir or placebo) will be labelled with identical labels including: the protocol identifying number, Hospital Universitari Germans Trias i Pujol, subject number in the clinical trial, administration route, XX tablets of RAL or placebo, posology: 2 tablet/24 h, coordinator investigator, sponsor, store at room temperature, batch number, expiration date and "for clinical trial use only". They will be storage at the Pharmacy Service of Germans Trias i Pujol Hospital.

### 5.4.4 Unblinding procedures

When the investigator or sub-investigator needs to identify the drug used by a subject and the dosage administered in case of emergency e.g., the occurrence of serious adverse experiences, he/she will contact the un-blinded correspondent in the center and make

a request for emergency unblinding. As requested by the investigator or sub -investigator the un-blinded correspondent will provide the information to him/her promptly and report unblinding to the sponsor. The un-blinded correspondent will make a record promptly however, the investigator or sub-investigator must enter the intensity of the adverse experiences observed, their relation to study drug, the reason thereof, etc., in the medical chart etc., before unblinding is performed.

In the event that unblinding has occurred, the circumstances around the unblinding (e.g., date and reason) must be documented promptly, and the Monitor notified as soon as possible. Only the principal investigator or

delegate and the respective subject's code should be unblinded. Trial site personnel and Sponsor personnel directly associated with the conduct of the trial should not be unblinded.

## 5.5 FORESEEN CALENDAR

- Clinical trial submission: October 2016
- First patient first visit: December 2016
- Inclusion period: 36 weeks
- Follow-up period: 48 weeks
- Last patient last visit: 30/09/2018 (End of study)
- Final report submission: September 2019

## 5.6 END OF TRIAL

The date of the end of the trial will be to the last visit of the last patient.

The trial will be prematurely stopped if there are withdrawals because of intolerance or toxicity more than 20%.

If the study must be interrupted prematurely, all non-used materials should be returned to the sponsor, at the *Lluita Contra la SIDA Foundation*. The principal investigator will keep the investigator file and a copy of the completed CRF.

In case there were no patients included in the study, the sponsor will take care of all materials.

## 5.7 SOURCE DATA

Source documents are the patient's medical records, the results obtained through blood tests as routine clinical and laboratory results obtained from blood samples and fecal samples collected on the same day that the blood test.

Study data will be collected through a Case Report Form (CRF).

## 6 TRIAL INVESTIGATIONAL PRODUCT(S)

### 6.1 EXPERIMENTAL AND CONTROL TREATMENTS

Study treatment consists to intensify current ART with reformulated raltegravir 1200 mg QD versus placebo:

- Raltegravir arm: Current ART + Raltegravir 1200 mg. It is an antiretroviral drug used in general HIV management. The formulation of the active principal components corresponds to the non-marketed formulation.
- Placebo arm: Current ART + RAL-placebo: The placebo was created by Merck Sharpe & Dohme co. to match the active product.

### 6.2 SUPPLY, PACKAGING, LABELING AND STORAGE

The investigator shall take responsibility for and shall take all steps to maintain appropriate records and ensure appropriate supply, storage, handling, distribution and usage of investigational product in accordance with the protocol and any applicable laws and regulations.

All antiretroviral treatments will be administered by the Pharmacy Service of the participating sites.

Clinical Supplies will be provided by the Merck Sharpe & Dohme co. as follows:

#### Bottle ID Product Name & Potency Dosage Form

- Reformulated raltegravir 600 mg (Film-coated Tablet)
- Placebo to match reformulated raltegravir 600 mg (Film-coated Tablet)

Reformulated raltegravir/placebo will be sent to the Pharmacy Service of site, where reception, units, batch number and expiration date will be confirmed. The investigational medication will be supplied and labeled under GMP in order to support a double-blind trial and in compliance with regulatory requirements. No conditioning nor labeling will be required in the Pharmacy Service.

All investigational products will be storage at the Pharmacy Service of Germans Trias i Pujol Hospital.

It is not required special storage conditions.

### 6.3 DOSE, INTERVAL, ROUTE AND METHOD OF ADMINISTRATION

The route of study drug administration is oral.

- Reformulated Raltegravir 1200 mg (2 tablets at the same time x 600mg) once daily plus current ART during 48 weeks from randomization.
- RAL- Placebo (2 tablets at the same time of placebo) once daily plus current ART during 48 weeks from randomization.

Reformulated raltegravir/placebo can be taken with or without food.

If a subject misses a dose and it is less than 12 hours before the next dose, the missed dose should be skipped and the normal dosing schedule resumed. The subject should not double the next dose in order to compensate for what has been missed.

Acceptable antiretroviral drugs in the background regimen will include a PI boosted with cobicistat/ritonavir or NNRTI/NRTI based 3-drug ART.

#### **6.4 DRUG ACCOUNTABILITY**

No returned drug accountability will be performed.

To perform the drug accountability of the dispensed product, the records of the Pharmacy Service of the site will be used.

#### **6.5 ARM DESCRIPTION**

Patients will continue on their usual antiretroviral regimen and at randomization moment will be added during 48 weeks reformulated raltegravir or placebo according to randomization. The rest of the antiretroviral treatment will remain unchanged.

- RAL arm: ongoing ART + RAL 1200 mg QD (2 x 600 mg)
- Placebo arm: ongoing ART + RAL placebo QD (2 tablets of RAL placebo)

#### **6.6 MODIFICATION OF THE TREATMENT REGIMEN**

No changes in treatment regimes are foreseen during the study period, except changes in the antiretroviral regimen as the NRTI/NNRTI by PI/r/c or the PI/r/c by NRTI/NNRTI.

In case of failure of one of the regimens, a new regimen will be decided using a resistance test.

In case adverse events to the medication occur, the investigator will decide if it is necessary to replace it.

At the end of the study, the change of treatment will be done at the discretion of the physician.

#### **6.7 CONCOMITANT TREATMENTS**

All other treatments, including over the counter treatments, apart from the study medication which is administered during the study period will be considered concomitant treatments and should be documented in the CRF.

It is remembered that the patients who participate in the study should not continue any concomitant treatment without the knowledge and permission of the investigator.

All participants will be discouraged to initiate any concomitant treatment with antibiotics, nutritional supplements, or drugs that modulate immunity. Subjects requiring some of these treatments for their clinical management during follow-up will not be excluded from the analyses, but the type, duration and reasons for intake will be recorded and taken into account in association analyses.

In the IMPD/IB of the IMP (appendix I - II), detail on pharmacological interacions and dose recomendations with other drugs are specified.

#### **6.8 COMPLIANCE**

Treatment adherence will be self-reported by the patient by answering the adapted SERAD questionnaire (included in the CRF).

The investigator is to ask the patient about treatment adherence to antiretroviral and concomitant treatment and this data is to be written in the clinical record. This data is to guarantee the compliance.

No pill count will be performed to assess compliance.

## **7 SELECTION AND WITHDRAWAL OF SUBJECTS**

### **7.1 INCLUSION CRITERIA**

1. Age  $\geq$ 18 years old
2. Documented HIV infection
3. Stable 3-drug antiretroviral treatment including PI/r/c or NNRTI for at least 6 months.
4. Plasma HIV-1 RNA load  $<50$  copies/mL for at least 12 months.
5. Signed Informed Consent

### **7.2 EXCLUSION CRITERIA**

1. PI/r monotherapy
2. INSTI therapy during the previous 6 months
3. Evidence of previous INSTI resistance
4. Creatine clearance  $<50$  mL/min
5. Child-Pugh B or C
6. History of active uncontrolled GI disorders or diseases including:
  - 6.1. Major surgery of the GI tract, with the exception of cholecystectomy and appendectomy, in the previous 5 years.
  - 6.2. Any major bowel resection at any time
  - 6.3. Any chronic digestive disease such as peptic ulcer, Crohn's disease, ulcerative colitis, coeliac disease, confirmed intolerance to lactose or indeterminate colitis.
  - 6.4. Persistent infectious gastroenteritis, colitis or gastritis; persistent or chronic diarrhea of unknown etiology; *Clostridium difficile* infection (recurrent) or *Helicobacter pylori* infection (untreated);
  - 6.5. Irritable bowel syndrome (moderate-severe)
  - 6.6. Chronic constipation
  - 6.7. Active proctitis
7. Antibiotic therapy within the previous 2 months
8. In women, pregnancy or breastfeeding\*.

\* Female subjects of childbearing potential must not be pregnant, not be planning a pregnancy or breastfeeding. Sexually active women must be willing to use an effective method of contraception (hormonal contraception, diaphragm, intra-uterine device (IUD), or anatomical sterility in self or partner) from baseline until the end of the clinical trial. Sexually active men in heterosexual relationships must be willing to use an effective method of contraception (anatomical sterility in self) or agree on the use of an effective method of contraception by his partner (hormonal contraception, diaphragm, intra-uterine device, or anatomical sterility) from baseline until the end of the clinical trial.

*\* condom use is considered as an additional method of contraception only and cannot be the only method of contraception used as not been considered an effective method by the Clinical Trial Facilitation Group (CTFG) guidelines.*

### **7.3 SUBJECT WITHDRAWAL CRITERIA**

#### **7.3.1 Early subject withdrawal**

The patients will complete the clinical study before the stipulated time in the following circumstances:

- Virological failure: it is defined as  $\geq$  200 copies/mL in 2 consecutive determinations, or a single HIV-1 RNA values  $> 1000$  copies/mL.
- Interruption of treatment due to adverse events, intolerance or poor adherence during the study.

- Concurrent process or illness which in the opinion of the investigator requires the withdrawal of the patient.
- Protocol deviation which in the opinion of the sponsor requires the withdrawal of the patient.
- The patient withdraws consent to participate in the study.
- Other

### **7.3.2 Medical approach to withdrawal**

In all cases, 'end of study form' is to be filled. Detailed information will be given about the date and reasons of the discontinuation to the sponsor. The investigator will facilitate the necessary medical support.

### **7.3.3 Follow-up after early withdrawal**

That is, as a general rule, all patients who discontinue treatment prematurely will undergo a clinical examination and all tests specified in the visit.

In the presence of virological failure, the new antiretroviral treatment regimen will be constructed based on the physicians' criteria.

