### 5.3 ENDPOINTS

#### 5.3.1 Primary endpoint(s)

- Increase in bacterial richness (observed species) at week 48, relative to baseline (week 0).

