## 8.2 TRIAL DEVELOPMENT

After accepting the participation and meeting selection criteria during the screening visit, patients would be assessed the baseline visit. Study visits would be at screening, entry (BL) and weeks 12, 24 and 48. Visits should be performed within a 2-weeks window.

Blood and fecal specimens will be obtained and stored at the points specified in the flow chart of the study.

Plasma samples and PBMC will be stored at -80°C.

Viral load, CD4 cells count and a complete biochemistry and hematology will be performed at all visits.

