## 8.4 LABORATORY TESTS

Patients will fast for at least 8 hours prior to assessment, in the points specified in the flow chart of the study (section 8.5). The following parameters will be quantified, as needed:

- **Blood count:**
  - Hemoglobin
  - Red blood count
  - Hematocrit
  - White cell blood count
  - Neutrophil count
  - Lymphocyte count
  - Platelets
  - Prothrombin time
- **Blood biochemistry:**
  - Albumina
  - Glucose
  - Urea
  - Creatinine
  - Estimated glomerular filtration rate (CKD-EPI)
  - Ionogramme: sodium, potassium
  - Total Bilirubin
  - Cholesterol (HDL, LDL and total)
  - Triglycerides
  - Liver enzymes: aspartate aminotransferase (AST), alanine aminotransferase (ALT), gamma-GT, alkaline phosphatase
- **Pregnancy test in women (test strip)**

- **Immunology:**
  - CD4 lymphocytes count
  - CD4 lymphocytes percentage
  - CD8 lymphocytes count
  - CD8 lymphocytes percentage
  - CD4/CD8 ratio
  - HLA-DR
- **Virology:** Plasma HIV-1 viral load.
- **Genotypic testing in plasma at virological failure.**
- **Whole blood:** a blood sample (5 x 10 mL EDTA tubes will be collected at each visit, from which irsiCaixa will obtain 4 plasma vials and as many PBMCs as possible). Plasma markers will be assessed by Luminex and or ELISA technology using EDTA-plasma samples. PBMC-associated markers will be analyses using multicolor flow cytometry. In all cases cryopreserved samples, will be stained and acquired on a Fortesa (BD Biociences) cytometer and analyzed using commercial (Flow Jo) and on-site developed software (Ourflow). In case of changes in the microbiome, the quantification of viral reservoir will be done in PBMCs.
- **Stool samples** will be collected at each visit. This will allow accounting for natural variation in gut microbiota composition. Samples will be used for taxonomic and functional / metagenomic analysis of the bacterial and viral microbiome and soluble & cellular markers of immune activation, inflammation and bacterial translocation.

**Note: Before the beginning of the study, all labs will facilitate to the sponsor and to the investigator a list of the reference normal values of the parameters assessed.**

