### 10.1 STATISCAL ANALYSIS

- Taxonomic and functional diversity within (alpha-diversity) and between samples (beta-diversity) will be determined. Rarefaction curves will be generated to evaluate sampling efficiency. Diversity measures, reflecting the richness of the microbiome in terms of number of species and abundance of each species will be calculated. This will enable comparisons between groups and timepoints. Ordination methods including principal component analysis and phylum abundance within individuals will be used to check for significant differences between groups. Bacterial abundance and functional profiles will be analyzed with LEFSe. Univariate correlations involving >2 groups will be done applying ANOVA plus Tukey-Kramer post-hoc tests and Benjamini-Hochberg correction; 2-group comparisons will be performed with the Welch's t-test. The relationship between the microbiome and markers of immune activation, inflammation, tissue damage and bacterial translocation will require the application of nonlinear Kernel regression methods.
- Subjects requiring antibiotics for their clinical management during follow-up will not be excluded from the analyses, but the type, duration and reasons for antibiotic intake will be recorded and taken into account in association analyses. Results in HIV-1-infected subjects will be compared to the gut microbiome profiles of healthy HIV-1-negative individuals previously reported by the EU FP7-funded MetaHIT consortium. We will also use microbial ecology theory to describe ecological networks between microbes and between them and the host (degree distribution, clustering coefficient, distance, centrality, community structure, connectivity index, etc.).

*For extensive examples of microbiome analyses available and performed previously by our group at irsiCaixa, please see: Noguera-Julian, M. et al. Gut microbiota linked to sexual preference and HIV infection. EBioMedicine (2016) <http://dx.doi.org/10.1016/j.ebiom.2016.01.032>.*

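### Stopping treatment ends study participation, so patients who leave before week 46 have no week-48 stool and drop out of the primary comparison

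*Combined protocol and SAP*

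**What the plan says.** Section 7.3.1 opens its list of withdrawal events with "The patients will complete the clinical study before the stipulated time in the following circumstances". The list includes virological failure and "Interruption of treatment due to adverse events, intolerance or poor adherence during the study". The rule therefore ends participation in the study, not only intake of study drug. Section 7.3.2 confirms this: "In all cases, 'end of study form' is to be filled".

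Section 7.3.3, on follow-up after early withdrawal, states that "all patients who discontinue treatment prematurely will undergo a clinical examination and all tests specified in the visit". It does not say which visit is meant and sets no later contact. Section 7.3.4 replaces only patients withdrawn for a protocol deviation.

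The primary endpoint (5.3.1) is "Increase in bacterial richness (observed species) at week 48, relative to baseline (week 0". Section 8.2 sets the schedule: "Study visits would be at screening, entry (BL) and weeks 12, 24 and 48", each with a two-week window. Stool samples, according to 8.4, "will be collected at each visit. This will allow accounting for natural variation in gut microbiota composition". The flow-chart in 8.5 ticks stool at baseline and weeks 12, 24 and 48. It has no early-discontinuation column, and its virological-failure column ticks only viral load and genotyping.

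Section 10.1 keeps antibiotic users in the analysis. It gives no rule for patients who stop, and no section defines an analysis set or a missing-data method. On tests it says that "2-group comparisons will be performed with the Welch's t-test", without naming a time point.

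**The concern.** Randomisation makes the two arms comparable at baseline. A comparison restricted to patients who reach week 48 keeps that property only if leaving is unrelated to arm or to outcome. Exits for adverse events, intolerance or poor adherence happen after randomisation, and their frequency or causes may differ between raltegravir and placebo. Patients who leave may also differ in richness from those who stay.

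Here the loss comes from a written rule. A patient who stops tablets at week 10 and would willingly give a stool sample at week 48 is not asked for one. The primary endpoint then cannot be computed for that patient. With 40 and 20 patients per arm, even balanced losses cost some precision.

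**Working it through.** **Inputs from the plan.** 60 patients, 40 raltegravir and 20 placebo (5.2, 10.2); stool at four visits (8.5); window of two weeks either side (8.2, 8.5). The plan states no expected stop rate, no SD of the change in richness and no sample size calculation, so it has no figure to reproduce beyond the 2:1 split: 60 × 2/3 = 40 and 60 × 1/3 = 20.

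**Assumptions.** Stop rate p of 5% to 20%; gap d of 0.5 to 1 SD between completers and leavers; fraction r (0 to 1) of the drug effect that a stopper still has at week 48.

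**1. Who is affected.** The window opens at week 48 − 2 = 46, which is 46/48 = 95.8% of the treatment period. Any exit before then leaves no week-48 value. At 5%, 0.05 × 60 = 3 patients; at 20%, 0.20 × 60 = 12.

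**2. Precision.** In SD units, SE of the difference = √(1/n₁ + 1/n₂).

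| Patients at week 48 | SE | Change |
|---|---|---|
| 40 and 20 | √(1/40 + 1/20) = 0.274 | reference |
| 38 and 19 (5% lost) | √(1/38 + 1/19) = 0.281 | +2.6% |
| 32 and 16 (20% lost) | √(1/32 + 1/16) = 0.306 | +11.8% |

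**3. Bias.** If leavers lie d below completers, the completers' mean exceeds the whole-arm mean by p × d. With the same d in both arms, bias = (p_RAL − p_PBO) × d.

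- 10% against 5%: 0.05 × 0.5 = 0.025 SD; 0.05 × 1 = 0.05 SD.
- 20% against 5%: 0.15 × 0.5 = 0.075 SD; 0.15 × 1 = 0.15 SD.
- Equal rates and equal gaps: 0.

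Against an SE of 0.274 SD, the non-zero values are 0.025/0.274 = 9% to 0.15/0.274 = 55% of one standard error.

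**4. What retaining stoppers does to signal-to-noise.** Take an on-drug effect of 1 and the same stop rate in both arms. At 20% stopping, using only those who reach week 48 gives 1/0.3062 = 3.266. Using everyone gives (0.8 + 0.2r)/0.2739:

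- r = 0: 2.921, which is −10.6%;
- r = 1: 3.651, which is +11.8%;
- break-even at r = (0.2739 × 3.266 − 0.8)/0.2 = 0.47.

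At 5% stopping the reference is 1/0.2810 = 3.559, and the range is 0.95/0.2739 = 3.469 (−2.5%) to 3.651 (+2.6%).

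**The case against.** The strongest case is that this is a pilot exploratory study asking what raltegravir does while it is taken, so ending follow-up when drug stops fits the question. Off-drug stools may also weaken the signal. Section 3 reports that immune effects of raltegravir intensification reverted after withdrawal. That is T-cell and not microbiome evidence, but it points to the unfavourable end of step 4. After virological failure, 7.3.3 also allows a new regimen, so a later stool would partly reflect other drugs. All this stands. It is why the on-treatment analysis belongs alongside and why no gain in power is claimed. It does not remove the selection problem: a completers-only comparison is not a clean on-drug comparison either. The pilot label explains the missing sample size calculation, not the missing rule for leavers.

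Some stronger readings do not hold:

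- *No stool is taken at exit.* Sections 7.3.3 and 8.4 together make an exit stool the natural reading. The virological-failure column in 8.5 has no clinical-visit or adverse-event tick and looks like add-on virology. The text should simply say so.
- *The bias cannot be checked at all.* Baseline stools, any week-12 or week-24 stools taken before exit, probably an exit stool, and the recorded date and reason for stopping (7.3.2) allow stoppers and completers to be compared by arm. Only the week-48 value is out of reach, so the check is partial.
- *The plan excludes stoppers, or fixes a Welch test at week 48.* Section 10.1 does neither. The restriction to those who reach week 48 follows in practice from the missing samples.
- *Every adverse event ends participation.* Section 6.6 lets the investigator replace medication after one.

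**Conclusion.** The concern holds as a design weakness worth correcting, not as a fatal flaw. A stated rule gives up primary-endpoint data after randomisation, for reasons that may differ by arm, in patients who might still consent to a sample.

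Its size is unknown. The ranges of 3 to 12 missing patients, 2.6% to 11.8% loss of precision and 0 to 0.15 SD bias rest wholly on assumed stop rates and gaps. The largest bias needs both 20% against 5% stopping and a full 1 SD gap. A reader might take the 20% in 5.6 as the expected rate. It is only the level of withdrawals for intolerance or toxicity above which the trial stops.

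A reader might also infer that the sponsor's result will be biased, or that retaining stoppers will raise power. The documents support neither: bias is zero with equal rates and gaps, and signal-to-noise may move either way.

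**What to change.** - **7.3.1 and 7.3.3:** separate stopping study drug from leaving the study. Stoppers keep at least the scheduled week-48 stool and research blood, unless consent is withdrawn or another section requires termination (for example pregnancy, 9.7).
- **7.3.2 and 7.3.4:** complete the end-of-study form when the patient leaves the study, not when drug stops, and align the replacement rule.
- **7.3.3 and 8.5:** state that the exit visit includes stool and research blood, and add a column for it.
- **10.1:** report the week-48 change by randomised arm in all patients with a week-48 stool, on or off study drug, with an on-treatment analysis alongside.

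Cost: text changes in these sections; about 3 to 12 retained visits at 5% to 20% stopping, fewer if some do not return, all already planned for the 60 patients; and at most 3 to 12 exit stools on top of 60 × 4 = 240 (1.3% to 5%). The all-randomised estimate may be diluted, by 5% to 20% if stoppers lose the whole effect. This remains an analysis of available cases: patients who withdraw consent or are lost are still missing, and 10.1 should say how they are reported.
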